5.8.3 Clinical Laboratory Assessments

Clinical laboratory tests (CBC, CMP, and/or lipid profile) will be performed at the Screening Visit and at Day 15 or withdrawal. Per the protocol amendment, version 02, basic metabolic panels will be performed at Day 3 and Day 8.

Clinical laboratory test parameters, with associated reference ranges provided by the laboratory, will be listed by cohort, subject and treatment. Clinical laboratory test results will be indicated as normal or abnormal (high, low). Mean change (baseline to Day 15) for CPK, ALT and AST in each dosing cohort will be summarized by cohort and by final IV treatment. For other clinical laboratory test parameters, observed values change from baseline will be also summarized for cohorts and final IV treatments.

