7 STUDY ENDPOINTS

- To support a dose of atorvastatin injection that adequately replaces oral atorvastatin, the following primary endpoint will be evaluated for each of the three, labelled oral doses of atorvastatin (10, 20, and 40 mg daily); endpoints are assessed using the subjects' levels of (LDL-C) and high-density lipoprotein cholesterol (HDL-C):
 - Eleven or more subjects in a dosing cohort of thirteen with a Day 15 LDL-C not more than 125% of their baseline LDL-C.

Secondary endpoints that contribute to the same objective are as follows:

- Eleven or more subjects in a dosing cohort of thirteen with a Day 15 HDL-C not less than 75% of their baseline HDL-C.

- The mean change in LDL-C at Day 15 for each treatment cohort (N=13)
- To compare the pharmacokinetic profile of atorvastatin administered by the intravenous route to that of oral administration, the following parameters of atorvastatin, 2-hydroxy atorvastatin and 4-hydroxy atorvastatin will be calculated for each of the three final IV treatment cohorts (See [Study Design](#) for description of the three cohorts):
 - Maximum serum concentration (C_{max})
 - Area under the curve to infinity (AUC_{inf})
 - Area under the curve to 24 hours (AUC_{0-24})
 - Elimination half-life ($T_{1/2}$)
 - Volume of distribution at steady state (VD_{ss})
 - elimination rate constant (K_{el})
 - Clearance (Cl)
- To explore the pharmacokinetic profile of atorvastatin administered by the subcutaneous route, the following parameters of atorvastatin, 2-hydroxy atorvastatin and 4-hydroxy atorvastatin will be calculated for each of the three final treatment cohorts (See [Study Design](#) for description of the three cohorts):
 - C_{max}
 - AUC_{inf}
 - AUC_{0-24}
 - $T_{1/2}$
 - VD_{ss}
 - K_{el}
 - Cl/F
 - Cl
- To assess the safety of the study drug, the following will be evaluated:
 - Adverse events
 - Mean change (baseline to Day 15) for creatine phosphokinase (CPK), alanine aminotransferase (ALT) and aspartate aminotransferase (AST) in each dosing cohort.

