9.3 Key Study Procedures

9.3.1 Clinical Laboratory Assessments

Blood sample collection for routine laboratory assessments will be performed within protocol-specified time periods and according to the site's standard practices for drawing and processing samples. The analytes listed here in Table 9-2 are measured by the site's local laboratory and evaluated by the investigator for safety monitoring with respect to reference ranges provided by that lab:

Table 9–2a. Clinical Lab Analytes to be Measured at Screening, Lead-in End Visit and Day 15

Complete blood count (CBC) with differential	
Hematocrit	Neutrophils, absolute count
Hemoglobin	Lymphocytes, absolute count
Total white blood cell count	Monocytes, absolute count
Platelet count	Eosinophils, absolute count
	Basophils, absolute count
Comprehensive Metabolic Panel (CMP)	
Sodium	Albumin
Potassium	Total protein
Chloride	Aspartate aminotransferase (AST)
Total carbon dioxide (serum bicarbonate)	Alanine aminotransferase (ALT)
Glucose	Alkaline phosphatase (ALP)
Blood urea nitrogen (BUN)	Total bilirubin
Serum creatinine (SCr)	Creatine Kinase (CK)
Calcium	Lactate Dehydrogenase (LDH)
Lipid Profile	
Low-density lipoprotein cholesterol (LDL-C)	Total cholesterol
High-density lipoprotein cholesterol (HDL-C)	Triglycerides

b. Clinical Lab Analytes to be Measured at Day 3 and Day 8

Basic Metabolic Panel	
Blood urea nitrogen (BUN)	Aspartate aminotransferase (AST)
Serum creatinine (SCr)	Alanine aminotransferase (ALT)
Creatine Kinase (CK)	Alkaline phosphatase (ALP)
LDL-C (Day 8 only)	

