9.4.4 Description of Treatment Period

The subject presents to the clinic for daily outpatient visits during the 15-day treatment period. The subject is monitored in the clinic for a minimum of approximately 15 minutes after any injection to ensure there are no issues with bleeding or other adverse reactions.

Spontaneously-reported adverse events are recorded in addition to any changes in concomitant treatments.

9.4.4.1 Day 1

Vitals are taken between 30 and 0 minutes before the start of the first IMP injection.

The Investigator's standard technique and equipment are used to prepare the injection site and delivering the injection. If any IV tubing is utilized, normal saline is used to flush the line immediately following the injection of IMP.

Vital sign measurements are repeated at 15 (\pm 5) minutes after the time of the IMP administration.

9.4.4.2 Days 2, and 4 through Day 7

The subject returns to the clinic each day at the approximate same time of day for an outpatient visit. The subject receives an injection of atorvastatin at the same amount and by the same route and method as at the Day 1 visit.

9.4.4.3 Day 3

Blood is drawn prior to the daily injection of study drug and submitted to the site's local laboratory to measure the analytes listed in [Table 9-2b](#). Levels of liver and muscle enzymes are reviewed against baseline values to assess safety.

9.4.4.4 Day 8

Prior to administration of the daily injection of atorvastatin, a blood sample is collected, processed and analyzed at the Investigator's local laboratory to provide an LDL-C level. Additionally, the analytes listed in [Table 9-2b](#) are measured. Levels of liver and muscle enzymes are reviewed against baseline values to assess safety.

LDL-C levels are transmitted to the sponsor as soon as available.

9.4.4.5 Days 9 through 14

The subject returns to the clinic each day at the approximate same time of day for an outpatient visit. The subject receives an injection of atorvastatin at the same amount and by the same method as at the Day 1 visit

9.4.4.6 Day 15

Unless withdrawn early from the treatment period (See [Section 9.4.4.7](#)), the subject presents to the clinic on Study Day 15 for their final injection with atorvastatin.

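### CPK, ALT and AST are tabulated only as change to Day 15, so the plan gives no rate of enzyme excursions by dose and route

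*SAP*

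**What the plan says.** The protocol's safety endpoint for these enzymes (section 7) is "Mean change (baseline to Day 15) for creatine phosphokinase (CPK), alanine aminotransferase (ALT) and aspartate aminotransferase (AST) in each dosing cohort". SAP section 3 and SAP 5.8 repeat it, and SAP 5.8.3 specifies the table: "Mean change (baseline to Day 15) for CPK, ALT and AST in each dosing cohort will be summarized by cohort", and also by final IV treatment.

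The enzymes are measured more often than that. Protocol Table 9-2, part b ("b. Clinical Lab Analytes to be Measured at Day 3 and Day 8"), includes CK, AST and ALT. Protocol 9.4.4 gives the purpose of both draws: "Levels of liver and muscle enzymes are reviewed against baseline values to assess safety". The SAP acknowledges them in 5.8.3: "Per the protocol amendment, version 02, basic metabolic panels will be performed at Day 3 and Day 8".

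For subjects who stop early, the SAP provides for a panel: "Clinical laboratory tests (CBC, CMP, and/or lipid profile) will be performed at the Screening Visit and at Day 15 or withdrawal". Individual results are reported too: "Clinical laboratory test parameters, with associated reference ranges provided by the laboratory, will be listed by cohort, subject and treatment". Each result is marked normal, high or low.

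**The concern.** Protocol 5.5 describes rhabdomyolysis as rare but serious, and Protocol 5.1 notes raised liver enzymes at the highest nonclinical doses. Both are risks to individual subjects. A mean change at one visit, over 10 to 13 people, is a weak way to describe such a risk, and a value taken only at Day 15 cannot show a peak at Day 3 or Day 8.

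The trial is also dose-ranging. A cohort can be closed and reopened at another dose (Protocol 9.3.6.2.2), and subjects still on treatment are then withdrawn (Protocol 9.4.4.7). SAP 5.6 summarises efficacy for the final IV daily dose and for each IV daily dose. SAP 5.8.3 summarises enzymes by cohort and final IV treatment only. At stake is whether the report can state how often enzymes rose, and by how much, at each dose and by each route.

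**Working it through.** The plan gives no figure for the enzyme summary, so there is nothing of its own to reproduce. The check is an inventory of planned outputs, followed by a labelled illustration.

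**Inventory for CPK, ALT and AST**

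| Possible output | Named in the documents? |
|---|---|
| Change to Day 15, by cohort and final IV treatment | Yes (SAP 5.8.3) |
| Safety data by route | In general terms (SAP 5.8) |
| Day 3 and Day 8 change | No |
| Maximum on-treatment value per subject | No |
| Shift table, or count above ULN or a multiple of it | No |
| By each IV daily dose received | No (done for efficacy, SAP 5.6) |
| Handling of a withdrawal value in the Day 15 summary | Not stated |
| By-subject listing with high/low flags | Yes (SAP 5.8.3) |
| SD, minimum, median, maximum alongside the mean | Yes (SAP 4.5) |

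Scheduled on-treatment draws are Day 3, Day 8 and Day 15. Two of the three have no named tabulation for these enzymes.

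**Illustration**

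- Inputs from the documents: n = 13 per IV cohort and n = 10 for the subcutaneous cohort (SAP section 4).
- Assumed inputs: one subject rises from b x ULN to k x ULN and the others do not change. The documents give neither ULN values nor enzyme levels, so a range is shown.
- Formula: mean change at Day 15 = (k - b)/n.

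| Rise still present at Day 15 | n = 13 | n = 10 |
|---|---|---|
| 0.5 to 3 x ULN | 2.5/13 = 0.19 | 2.5/10 = 0.25 |
| 0.5 to 5 x ULN | 4.5/13 = 0.35 | 4.5/10 = 0.45 |
| 0.5 to 10 x ULN | 9.5/13 = 0.73 | 9.5/10 = 0.95 |
| 1.0 to 5 x ULN | 4.0/13 = 0.31 | 4.0/10 = 0.40 |

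Three cases follow for the rise from 0.5 to 5 x ULN with n = 13:

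1. **Present at Day 15.** The mean moves by 0.35 x ULN, and the maximum change in the same table is 5 - 0.5 = 4.5 x ULN. A reader who looks at the maximum will see it.
2. **Present on Day 3 or Day 8, resolved by Day 15.** That subject's Day 15 change is 0, so the mean, SD and maximum of the Day 15 table all miss the rise.
3. **Subject withdraws with the raised value.** If the withdrawal panel counts as Day 15, the mean moves by 4.5/13 = 0.35 x ULN. If it does not, the mean is taken over the other 12 and the contribution is 0. The SAP does not choose between these.

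**The case against.** The strongest reply is that individual safety information is well covered:

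- Every result is listed by subject with reference ranges and high/low flags, and with 10 to 13 subjects per final cohort the listings can be read directly.
- The summaries carry SD, minimum and maximum as well as the mean.
- An abnormal laboratory finding can be an adverse event (Protocol 11.1.1), and Day 15 changes judged clinically significant are reported as such (Protocol 9.4.4.6). SAP 5.8.2 tabulates treatment-emergent events by number and percentage.
- Day 3 and Day 8 enzymes are reviewed during conduct, and the medical monitor reviews biochemistry before a dose increase (Protocol 9.3.6.2.2).
- The table shells are a separate document (SAP 5.10) and may contain by-visit tables.

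Most of this stands, and it rules out three stronger readings:

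- **Individual excursions are left out of the report.** A reader might infer this, but the listings and adverse event tables contradict it.
- **Subjects who withdraw early are ignored.** They have an enzyme panel (Protocol 9.4.4.7; SAP 5.8.3) and belong to the Safety Population (SAP 5.1). Whether their value enters the Day 15 mean is unstated, which is not the same as excluded.
- **A closed cohort has no Day 15 values.** Only subjects still on treatment are withdrawn (Protocol 9.3.6.2.1 and 9.4.4.7). Those who have reached Day 15 keep their results.

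The reply does not supply a rate. Listings are not summaries, and a high flag does not separate a slight rise from a marked one. Adverse event capture depends on investigator judgement, with no numerical threshold stated. The Day 15 maximum cannot show an earlier peak. The shells cannot be checked here, so the finding concerns what the SAP text specifies.

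**Conclusion.** The point holds as a reporting gap, not a loss of data. The only tabulated summary named for CPK, ALT and AST is change from baseline to Day 15, by cohort and final IV treatment. It does not use two of the three scheduled on-treatment draws, gives no breakdown by each IV dose, and leaves the status of withdrawal values open. The report would therefore lack a stated frequency of enzyme excursions by dose and route.

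Severity is low. The enzyme levels in the illustration are assumed; the inventory is not, but it rests on the protocol and SAP text without the table shells.

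**What to change.** In SAP 5.8.3, for the Safety Population and by cohort, each daily dose received and route, add:

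- (a) change from baseline in CPK, ALT and AST at Day 3 and at Day 8;
- (b) each subject's maximum on-treatment CPK, ALT and AST over Day 3, Day 8 and Day 15 or withdrawal;
- (c) the number and percentage of subjects above the laboratory ULN, and above multiples of it that the SAP states in advance.

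State that withdrawal values are included in (b) and (c), and say whether they also enter the existing Day 15 mean. The multiples are reporting categories only and carry no rule for managing subjects. The protocol's 2 x ULN limit for AST and ALT is a screening exclusion (8.4.2.2), and neither document gives an on-treatment or CK threshold.

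The cost is one extra table from data already collected. Its denominators are small, 10 to 13 per final cohort, so counts should be shown beside percentages and read descriptively.

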5.8.4 Vital Signs Assessments

Vital signs (seated SBP, DBP, heart rate, respiration rate and body temperature) will be measured at the Screening Visit, between 30 and 0 minutes before the start of IMP and at 15 (+ 5) minutes after the start of IMP on Day 1.

Vital signs results will be listed by cohort, subject and treatment. Observed values and change from baseline to the one time point for vital signs will be summarized for cohort and final IV treatments.

5.8.5 Physical Examinations

A physical examination will be performed at the Screening Visit.

Physical examination results will be listed by cohort, subject and treatment.

5.9 Interim Analysis

No interim analysis is planned for this study.

5.10 Statistical Programming and Deliverables

All statistical analyses, tables and listings will be generated in SAS (version 9.3 or later) with appropriate documentation and programming validation. The table of contents of all tables, figures, and listings will be presented in a TFLs shell supplemental document.

5.11 Changes from Pre-Specified Analyses

5.12 Changes to the Planned Analysis

Any deviation(s) of consequence from the SAP during the data analysis will be documented and justified in an amended SAP and/or in the final report or addressed in a separate document, as appropriate.

6 Revision History

Version	Date	Comments
2.0	3/16/20	Updated per Amendment 3 04 September 2019.
